5.1.2 AE date imputation

AE end date imputation

1. If ‘month’ is missing, the end date will be set to the earliest of the (min (last visit date, last dose date), 31DECYYYY, and date of death).
2. If ‘day’ is missing, the end date will be set to the earliest of the (min (last visit date, last dose date), 31MONYYYY, and date of death).
3. If ‘year’ is missing or AE is ongoing, the end date will not be imputed.

AE start date imputation

Before imputing AE start date, find the AE start reference date.

- If the (imputed) AE end date is complete and the (imputed) AE end date < treatment start date then AE start reference date = min (informed consent date, earliest visit date).
- Else AE start reference date = treatment start date

After finding the AE start reference date:

1. If 'year' is missing, the date uncertainty is too high; therefore the imputed AE start date will be set to NULL.
2. If 'year' is less than the treatment start date 'year', the AE started before treatment; therefore:
 - a. If 'month' is missing, the AE start date will be set to 01JULYYYY.
 - b. If 'day' is missing, the AE start date will be set to 15 MONYYYY.
3. If 'year' is greater than the treatment start date 'year', the AE started after treatment; therefore:
 - a. If 'month' is missing, the AE start date will be set to 01JANYYYY.
 - b. If 'month' is not missing, the AE start date will be set to the later of (01MONYYYY, AE start reference date + 1).
4. If 'year' is equal to the treatment start date 'year'
 - a. If 'month' is missing, the AE start date will be set to the AE reference start date +1.
 - b. If 'month' is less than the treatment start 'month', the AE start date will be set to 15MONYYYY.
 - c. If 'month' is equal to or greater than the treatment start 'month', the AE start date will be set to the later of (01MONYYYY, AE start reference date+1).

If complete (imputed) AE end date is available and the imputed AE start date is greater than the (imputed) AE end date, imputed AE start date will be set to the (imputed) AE end date.

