### **9.5.2 Safety variables**

The safety assessments are listed below:

- Identified and potential risks
- AEs and SAEs
- Vital signs
- Laboratory evaluations
- ECG
- 24h urinary calcium and phosphate excretion (in a subset of patients)
- BMD (in a subset of patients)

The incidence of treatment emergent AEs (events started on or after the study treatment start date during Epoch 3 will be summarized by primary system organ class and preferred term. Summaries will also be provided by severity and relationship to study medication. The incidence of death, SAEs, and AEs leading to discontinuation will be summarized separately by primary system organ class and preferred term. The number and percentage of patients with AEs related to identified and potential risks will be summarized by treatment.

Laboratory data will be summarized by presenting shift tables, summary statistics of raw data and change from baseline and by flagging of notable values in data listings.

[figure not shown]
Other safety assessments (e.g., vital signs and ECG) will be summarized descriptively by treatment as appropriate. Data will be listed, notable values will be flagged, and other information collected will be listed as appropriate.

[figure not shown]
Summary statistics (n, mean, standard deviation, median, Q1, Q3, minimum, and maximum) will be provided by visit and treatment for the 24h urinary calcium, phosphate excretion and BMD from the sub-study, for measurement at each visit and change from baseline values.

The above analyses will be performed for the SAF for data collected during Epoch 3 for *Week 12 analysis*. For *End of study analysis*, these analyses will be carried out for data collected during Epoch 3 + Epoch 4.

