2.6.2.1 Adverse events (AEs)

Treatment emergent adverse events (TEAEs) during the double-blind period are defined as any AE with start date on or after the start date of the first dose of the study drug during the double-blind period.

The number and percentage of patients with the following types of treatment emergent adverse events during the double-blind period will be provided by primary SOC, PT and treatment group

in separate tables: AEs, SAEs, AEs leading to study drug discontinuation, AEs suspected to be study drug related, and AEs leading to study drug interruption. TEAEs during the double-blind period will also be summarized by primary SOC, PT, maximum severity and treatment group. The most common TEAEs ($\geq 10\%$ in any treatment group) during the double-blind period will be presented by PT in descending order of frequency in the investigational study drug arm, LIK066 50 mg qd.

The following rules apply to the above AE summaries:

- If a patient has multiple AEs within a primary system organ class during the double-blind period, the patient will be counted only once in that primary system organ class
- If a patient has multiple occurrences of an AE with the same PT during the double-blind period, this patient will be counted only once at that PT level.
- An AE with increased severity should be considered and recorded as a new AE.

All TEAEs during the double-blind period will be summarized descriptively by primary SOC, PT and treatment in the following subgroups: baseline LVEF $< 45\%$ vs. $\geq 45\%$.

All AEs will be listed at the individual patient level. The listings will include those AEs reported during the screening and run-in period, and AEs reported after study discontinuation for those who discontinue the study prior to the end of the study.

Deaths occurred during the double-blind period will be summarized descriptively (using number and percentage of patients) by primary SOC and principal cause of death. All deaths will be listed.

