5.1.3 Concomitant medication date imputation

CM end date imputation

1. If 'day' is missing and 'month/year' are non-missing then impute date as the earlier of (treatment end date, and 31MONYYYY).
2. If 'day/month' are missing and 'year' is non-missing then impute date as the earlier of (treatment end date, and 31DECYYYY).
3. If imputed end date is less than the start date, use the start date as the imputed end date.

CM start date imputation

1. If 'year' is missing, the start date will be set to one day prior to treatment start date.
2. If 'year' is less than treatment start 'year', the CM started before treatment. Therefore:

- a. If 'month' is missing, the start date will be set to 01JULYYYY.
- b. If 'month' is non-missing, the start date will be set to 15MONYYYY.
3. If 'year' is greater than treatment start 'year', the CM started after treatment. Therefore
 - a. If 'month' is missing, the start date will be set to 01JANYYYY.
 - b. If 'month' is non-missing, the start date will be set to 01MONYYYY.
4. If 'year' is equal to the treatment start date 'year'
 - a. If 'month' is missing or equal to the treatment start 'month', then the start date will be set to one day prior treatment start date.
 - b. If 'month' is less than the treatment start 'month', the start date will be set to 15MONYYYY.
 - c. If 'month' is greater than the treatment start 'month', the start date will be set to 01MONYYYY.

If complete (imputed) CM end date is available and the imputed CM start date is greater than the (imputed) CM end date, then imputed CM start date will be set to the (imputed) end date.

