5.2 AEs coding/grading

AEs will be coded according to MedDRA dictionary. The MedDRA version used for reporting will be described in the footnotes.

Safety topics of interest, defined in the Safety Profiling Plan are defined in the Program Case Retrieval Sheet. Missing severity will be assumed to be severe in the summary table.

Hypoglycemia classification is presented in Table 5-1.

Table 5-1 Hypoglycemia classification

Category	Definition	Criteria as specified in the Hypo eCRF
Severe hypoglycemia	An event, requiring assistance of another person (third party assistance) to actively administer carbohydrate, glucagon, or other corrective actions, confirmed or not by a BG measurement	An event with answer = 'YES' for any one of the two questions: 
• Was third party assistance required?• Was medical assistance received?

Category	Definition	Criteria as specified in the Hypo eCRF
Other clinically significant hypoglycemia	Plasma glucose < 3.0 mmol/l (54 mg/dl)* with or without typical symptoms of hypoglycaemia, and which is handled by the subject himself/herself.	An event with answer = 'YES' to the question 'Glucose measurement taken' and the plasma glucose < 3.0 mmol/l (54 mg/dl), and answer = NO to both questions: 
• Was third party assistance required?• Was medical assistance received?

*Blood glucose values need to be converted to plasma glucose values.

A plasma glucose of 3.0 mmol/L (54 mg/dL) corresponds to a whole blood glucose of 2.7 mmol/L (48 mg/dL)

Plasma glucose = blood glucose * 1.12.

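### Adverse events with no start year are given a NULL start date, and the SAP's literal definition of treatment-emergent then leaves out even those that are ongoing or ended after first dose

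*SAP*

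**What the plan says.** SAP 5.1.2 (AE date imputation) first derives a reference date. This is the earlier of consent and first visit if the event ended before treatment start, and treatment start otherwise. The numbered rules follow. Rule 1 covers a missing start year: "the date uncertainty is too high; therefore the imputed AE start date will be set to NULL". It does not use the reference date or the end date.

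SAP 2.6.2.1 (Adverse events) defines a treatment-emergent event as "any AE with start date on or after the start date of the first dose" of double-blind study drug and says nothing about a missing start date. Protocol 9.5.2 also relies on onset: "events started on or after the study treatment start date during Epoch 3".

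The main SAP tables report "The number and percentage of patients with the following types of treatment emergent adverse events during the double-blind period", covering "AEs, SAEs, AEs leading to study drug discontinuation, AEs suspected to be study drug related, and AEs leading to study drug interruption". The maximum-severity, most-common-event and LVEF-subgroup tables carry the same restriction. So does the general special-interest table in SAP 2.6.2.2, with its LVEF subgroup version.

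Missing severity is handled differently. SAP 5.2 states: "Missing severity will be assumed to be severe in the summary table".

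**The concern.** The two rules work against each other. One produces a NULL start date, and the other accepts only events whose start date passes a comparison. An event with an unknown start year that is ongoing, or that ended during treatment, therefore cannot enter the tables that carry most of the safety message.

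The effect runs in one direction. A real on-treatment event can be lost from these tables, and none can be added. That is the less cautious direction for safety reporting, and it matters most for rare risks, where one record can change a row. Lower limb amputation is the clearest example: it is on the special-interest list, and the SAP describes no separate table for it. An event recorded as the reason for stopping study drug could likewise be missing from the discontinuation table.

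**Working it through.** The documents state no figure for this rule, so there is none to reproduce. The check applies the SAP 5.1.2 start-date rules and then the SAP 2.6.2.1 definition (treatment-emergent = start date present and on or after first dose) to six cases.

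| Start date recorded | End date | Start date after SAP 5.1.2 | Treatment-emergent, literal reading | With fallback* |
|---|---|---|---|---|
| Year missing | Before first dose | NULL | No | No |
| Year missing | After first dose | NULL | No | Yes |
| Year missing | Ongoing | NULL | No | Yes |
| Treatment year, month missing | Ongoing | First dose + 1 day | Yes | Yes |
| Treatment year, month missing | Before first dose | Consent or first visit + 1 day | No | No |
| Treatment-start month, day missing | Ongoing | First dose + 1 day | Yes | Yes |

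*Fallback: a NULL start counts as treatment-emergent unless the end date is before first dose.

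- **Row 1.** Exclusion is correct, because the event ended before treatment.
- **Rows 2 and 3.** This is the gap. The closing step of SAP 5.1.2, which moves a start date back to the end date when it falls later, cannot act on a NULL.
- **Row 4.** Rule 4a deals with a closely similar uncertainty. It assigns the reference date plus one day, so the event is treatment-emergent unless its end date precedes first dose. Rows 3 and 4 differ only in whether the year was written down, yet one is dropped and the other counted.

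Size per affected patient, at the planned arm sizes (496 patients in ratio 1:1:2:2:2, Protocol 9.8):

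- Smaller arms: 496 × 1/8 = 62, and 1/62 = 1.6 percentage points.
- Larger arms: 496 × 2/8 = 124, and 1/124 = 0.8 percentage points.
- One to three such patients in an arm: 1.6 to 4.8 points (n=62) or 0.8 to 2.4 points (n=124).

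These shifts apply only when the patient has no other event qualifying for the same row, because SAP 2.6.2.1 counts each patient once per preferred term or organ class.

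There is one side effect. SAP 2.6.2.2 computes diarrhoea duration as end date minus start date plus one. With a NULL start this has no value, and no fallback is given.

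**The case against.** The best answer is that the trigger should hardly ever occur. Protocol 7.1 requires start and end dates with each AE and has events sought at every visit. Protocol 8.2 and 8.3 provide automatic checks and queries, 8.1 full verification of SAE documentation, and 7.2.2 SAE reporting within 24 hours of learning of the event. A study lasting up to 40 weeks leaves few records where even the year is unknown. This stands, and it is why the point is minor. The rule also applies to all arms alike, and no between-arm bias is shown.

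The introduction to SAP Section 5 also defers imputation details to programming specifications that are not among the documents. Those might classify NULL starts. A reader should therefore not infer that such events can never be treatment-emergent. The supported statement is narrower: the SAP states the NULL rule outright, gives no classification for it, and its definition as worded excludes it. An unseen specification does not repair that text.

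Three other inferences go too far:

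- **That every safety table is affected.** The adjudicated and site-reported ketoacidosis summaries and the clinically significant hypoglycaemia summaries (SAP 2.6.2.2) state no treatment-emergent condition. The deaths table depends on death within the double-blind period, and all AEs are listed.
- **That an end date after first dose proves on-treatment onset.** AEs are collected from study consent, and screening plus run-in lasts about four weeks. A run-in event may resolve on treatment and is then rightly not treatment-emergent.
- **That the medication rule is a cautious precedent.** For a missing year, SAP 5.1.3 says "the start date will be set to one day prior to treatment start date". Applied to AEs, that would also make them non-emergent.

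**Conclusion.** The point holds as a minor inconsistency in the SAP. Read literally, SAP 5.1.2 and 2.6.2.1 together remove events with no start year from the treatment-emergent AE, SAE, discontinuation, interruption, drug-related, severity, most-common and LVEF-subgroup tables, and from the general special-interest table. The exclusion is unwarranted as a default for events that are ongoing, ended on or after first dose, or have no usable end date. It is correct for those that ended before first dose. It is out of line with rule 4a and with the worst-case handling of missing severity.

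The number of affected records is unknown and probably very small. The shift of 1.6 or 0.8 points per patient assumes the planned arm sizes. The SAP was written after early termination, so if the analysed arms are smaller, each patient weighs more. Nothing in the documents shows that any event was actually lost.

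**What to change.** Add to SAP 2.6.2.1 or 5.1.2: *An AE with a NULL start date is treated as treatment-emergent unless its complete (imputed) end date is before the first double-blind dose.* Report the number of such events by arm, so that a reader can see whether the rule mattered.

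The cost is one sentence and one condition in the derivation. The downside is that an occasional run-in event of unknown onset may be counted as treatment-emergent, which is the cautious direction for a safety table. The condition uses only the end date, which Protocol 7.1 already requires. A condition based on the visit of first report would need an item that Protocol 7.1 does not list among the AE data.

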5.1.3 Concomitant medication date imputation

CM end date imputation

1. If 'day' is missing and 'month/year' are non-missing then impute date as the earlier of (treatment end date, and 31MONYYYY).
2. If 'day/month' are missing and 'year' is non-missing then impute date as the earlier of (treatment end date, and 31DECYYYY).
3. If imputed end date is less than the start date, use the start date as the imputed end date.

CM start date imputation

1. If 'year' is missing, the start date will be set to one day prior to treatment start date.
2. If 'year' is less than treatment start 'year', the CM started before treatment. Therefore:

- a. If 'month' is missing, the start date will be set to 01JULYYYY.
- b. If 'month' is non-missing, the start date will be set to 15MONYYYY.
3. If 'year' is greater than treatment start 'year', the CM started after treatment. Therefore
 - a. If 'month' is missing, the start date will be set to 01JANYYYY.
 - b. If 'month' is non-missing, the start date will be set to 01MONYYYY.
4. If 'year' is equal to the treatment start date 'year'
 - a. If 'month' is missing or equal to the treatment start 'month', then the start date will be set to one day prior treatment start date.
 - b. If 'month' is less than the treatment start 'month', the start date will be set to 15MONYYYY.
 - c. If 'month' is greater than the treatment start 'month', the start date will be set to 01MONYYYY.

If complete (imputed) CM end date is available and the imputed CM start date is greater than the (imputed) CM end date, then imputed CM start date will be set to the (imputed) end date.

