#### **5.5.6 Rescue medication**

During Epoch 3 and Epoch 4, rescue medication may be used in addition to ongoing study medication for those patients whose glycemic control is deteriorating. The patient must come in for an unscheduled visit to have a sample drawn for FPG and HbA1c measurement performed by the central laboratory if:

- Self-measured FPG on three consecutive occasions exceeds the limits in [Table 5-1](#).
- The FPG result from a blood sample analyzed at the central laboratory exceeds the limits described in [Table 5-1](#).

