2.4.2 Prior, concomitant and post therapies

Prior medications are defined as any recorded medication taken and stopped prior to the date of the first dose of the double-blind study drug.

Concomitant medications for the double-blind period are any medications given at least once between the day of first dose of double-blind study medication and the end of the double-blind period, including those which started pre-BL and continued into the treatment period.

Similarly, prior non-drug therapies are defined as any recorded non-drug therapy taken and stopped prior to the date of the first dose of the double-blind study drug. Concomitant non-drug therapies for the double-blind period are defined as any recorded non-drug therapy given between the day of first dose of double-blind study medication and the end of the double-blind period.

Prior and concomitant medications will be summarized separately by ATC, PT and treatment group. Prior and concomitant non-drug therapies will be summarized separately by primary SOC, PT and treatment group.

The number and percentage of patients meeting rescue criteria and taking rescue medication, and duration of exposure to rescue medication during double-blind period will be summarized by treatment group.

The number and percentage of patients on anti-diabetic medications at baseline (randomization visit) will be summarized by treatment group and medication types as follows:

- Any anti-diabetic medication (insulin or OADs)
 - Insulin
 - OADs (used as single pills)
 - Metformin
 - SU - Sulfonylureas (including Sulfonamides)
 - AGIs
 - TZDs
 - DPP-4 inhibitors
 - GLP-1 analogues
 - Combination of OADs
 - Phenformin + SU
 - Metformin + SU
 - Metformin + TZD
 - SU + TZD
 - Metformin + DPP-4 inhibitor
 - Metformin + AGI
 - DPP-4 inhibitor + TZD
 - Other

The search criteria for the anti-diabetic medications by type are included in [Appendix 5.5](#).

The use of prohibited medications, defined in [Table 2-2](#), will also be summarized.

Table 2-2 Prohibited medication for reporting

Prohibited Medication	Drug record No. or ATC
SGLT2 inhibitors	A10BK
Clarithromycin	00984601
Telithromycin	01548701
Itraconazole	00780701
Ketoconazole	00532501
Voriconazole	01510101
Posaconazole	01762801
Probenecid	00045101
Valproic Acid	00228501
Mefenamic Acid	00044201

The SAF will be used for the above analyses.

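### A partial rescue-medication start date can be imputed to the day before first dose, which the protocol rules out and which overstates rescue duration in the descriptive table

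*SAP*

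**What the plan says.** **The date rule (SAP 5.1.3).** For a missing year, "the start date will be set to one day prior to treatment start date". In the treatment-start year, if the month "is missing or equal to the treatment start" month, the same date is used: "the start date will be set to one day prior treatment start date". The other branches differ. In a later year, an unknown month becomes 1 January of that year. A known month after the first-dose month becomes the first of that month.

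**What it covers.** SAP 5.1.3.1 and 5.1.3.2 send prior and post therapies back to the same rule. SAP 5.1.1 covers study drug and 5.1.2 covers adverse events. SAP 2.4.2 defines concomitant medication as anything given at least once from first double-blind dose to the end of the double-blind period. Rescue medication meets that definition and is analysed in the same section.

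**The outputs.** In SAP 2.4.2, "duration of exposure to rescue medication during double-blind period will be summarized by treatment group". The same section states: "The number and percentage of patients on anti-diabetic medications at baseline (randomization visit) will be summarized by treatment group".

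**The protocol.** Section 5.5.6 states: "During Epoch 3 and Epoch 4, rescue medication may be used in addition to ongoing study medication". Rescue follows an unscheduled visit and central-laboratory confirmation, and is recorded on its own eCRF.

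**The concern.** Setting an uncertain start to the day before first dose is a reasonable default when the only question is whether a drug is prior or concomitant. It is a poor default for a duration, because it counts the longest exposure the treatment period allows. For rescue it also gives a date that cannot be true, since rescue is added to study drug already being taken. The SAP has no rescue-specific date rule, no rescue duration formula and no floor at Day 1.

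The rescue-duration summary is at stake, because readers use it as context for the HbA1c and FPG summaries. A second output may be exposed. If the programmers use imputed start dates to decide which anti-diabetic drugs were in use at baseline, a rescue drug dated to the day before first dose could be counted there.

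**Working it through.** The documents give no figure to reproduce, so the check applies the stated rule to example records. The rule is from SAP 5.1.3. The duration formula is the general one in SAP 2.1.1: end date minus start date plus 1. All calendar dates below are assumed.

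**Step 1. Worked records with a known stop date**

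| Case | First dose | True rescue | Missing | Imputed start | True days | Imputed days |
|---|---|---|---|---|---|---|
| 1 | 06 Mar 2017 | 27 Mar to 15 May 2017 | day | 05 Mar 2017 | 50 | 72 |
| 2 | 06 Mar 2017 | 12 Jun to 01 Sep 2017 | month | 05 Mar 2017 | 82 | 181 |
| 3 | 06 Mar 2017 | 12 Jun to 01 Sep 2017 | day only | 01 Jun 2017 | 82 | 93 |
| 4 | 06 Nov 2017 | 12 Feb to 01 Apr 2018 | month | 01 Jan 2018 | 49 | 91 |
| 5 | 12 Mar 2018 | 03 Sep to 18 Nov 2018 | month | 11 Mar 2018 | 77 | 253 |

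Case 1: 5 + 30 + 15 = 50 true days (March, April, May) against 27 + 30 + 15 = 72. Case 2: 19 + 31 + 31 + 1 = 82 against 27 + 30 + 31 + 30 + 31 + 31 + 1 = 181. A missing year in case 2 gives the same imputed date. Case 5 runs to Week 36 and is an extreme.

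Cases 3 and 4 are not pre-treatment. They show where the branch does not apply, although the first-of-month and 1 January conventions also lengthen duration.

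**Step 2. Bounds.** The overstatement is the true start minus the imputed start. With only the day missing in the first-dose month, the extreme is first dose on the 1st and rescue on the 31st, which gives 31 days. With the month missing in the treatment-start year, it can reach 252 days, the full 36 weeks.

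**Step 3. Cutting at Day 1.** Limiting exposure to the double-blind period removes one day: 72 becomes 71, 181 becomes 180 and 253 becomes 252. A floor at first dose + 1, as SAP 5.1.2 uses for an adverse event with an unknown month in the treatment-start year, removes two: 72 becomes 70 and 181 becomes 179. The impossible date goes, but nearly all the excess remains, because the excess comes from starting the clock at the beginning of treatment.

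**Step 4. How often the branch is reached.** A grid of every first-dose date in one calendar year by every rescue start from Day 1 to Day 252 gave:

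- Day missing: 6.2% pre-treatment, mean excess 10.8 days in those records. The mean over all day-missing records is 14.2 days, of which this branch supplies 0.062 × 10.8 = 0.67 day. The first-of-month convention supplies the rest.
- Month missing: 65.6% pre-treatment, mean excess 104.4 days in those records. The mean over all month-missing records is 97.2 days, of which this branch supplies 0.656 × 104.4 = 68.5 days.

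These figures assume uniform dates and full 36-week follow-up. The SAP says the study ended early, so they describe how the rule behaves and do not forecast this study's data.

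**The case against.** **Does the rule apply to rescue at all?** The rule is headed for concomitant medication, rescue has its own eCRF, and the SAP Appendix defers detail to programming specifications that are not supplied. This is the strongest objection. But the SAP defines concomitant medication by when a drug is given, not by the form it is recorded on, and rescue meets that definition. If the specifications hold a separate rescue rule, the SAP should refer to it.

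**How likely are such records?** Rescue follows an unscheduled visit and a laboratory confirmation, so a site that does not know the month or year should be unusual. This stands, and it limits the practical weight of the largest figures.

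**Stronger readings that a reader might infer, and that the documents do not support:**

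- *Every unknown month goes to the day before treatment.* This happens only in the treatment-start year. A later year gives 1 January.
- *The imputed date is before randomisation.* The anchor is first dose (SAP 2.1.1). If first dose is a day after randomisation, the imputed date is the randomisation day.
- *The error falls mainly on placebo and distorts the comparison.* Nothing in the documents gives rescue or missing-date rates by arm. More rescued patients in an arm would not in itself bias its mean duration more, and the number rescued does not depend on the start date.
- *The adverse-event rule always does the opposite.* It does so for a missing month or the first-dose month in the treatment-start year. A missing adverse-event year is left null.
- *Duration can only be lengthened.* That requires a known stop date. A partial stop date is capped at treatment end, which can cut off rescue that continued after study drug stopped.
- *The baseline anti-diabetic table is certainly wrong.* The SAP does not say that imputed dates decide who is on a drug at the randomisation visit.

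**Conclusion.** The point holds in this limited form. For a rescue record with a missing year, or with a missing month or the first-dose month in the treatment-start year, SAP 5.1.3 gives a start that the protocol makes impossible. With a known stop date, the reported rescue duration is too long: by no more than about a month if only the day is missing in the first-dose month, and possibly by many weeks if the month or year is missing.

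This rests on reading 5.1.3 together with the 2.4.2 definition, and on at least some rescue records having partial start dates. The documents give no count. If all dates are complete, the effect is nil. The consequence is confined to a descriptive rescue summary and, conditionally, the baseline anti-diabetic table. No NT-proBNP estimate or test uses these dates. It is a minor point, worth correcting because the remedy is cheap.

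**What to change.** Add to SAP 5.1.3, for Rescue Medication eCRF records with a partial start date:

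1. Use the date of the confirming central-laboratory sample if it is compatible with the recorded month and year.
2. Otherwise use the later of the first of the recorded month (if known) and first double-blind dose + 1 day. Never use a date before first dose.
3. If neither month nor year is known and there is no confirming sample, leave the duration missing and still count the patient as rescued.

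Where the year is known but the month is not, and no sample fits, the floor in item 2 would keep nearly all the excess (Step 3), and in a later year it would contradict the recorded year. Leaving the duration missing is the better choice there too. State the rescue duration formula in SAP 2.4.2.

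For the baseline anti-diabetic table, do not count a Rescue Medication eCRF record as in use at baseline solely because its start was imputed to first dose minus 1. Keep drugs whose recorded partial date clearly precedes V201.

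The cost is a few sentences and a small programming change. It needs no new assessments, since the protocol already requires the confirming sample. One limitation remains: protocol 5.5.6 places escalation of the background oral drug between confirmation and rescue, so the sample date may precede the true start and leave an excess equal to that interval.
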